**NOTES:**

1. For the purposes of this study, hospitalization is defined as any in-patient admission.
2. Hospitalizations occurring for the purpose of performing a planned procedure as per routine care such as implant procedures, or follow-up visits, are not to be reported as a SAE. However, complications or adverse events that occur during the planned procedure should be reported as (S)AEs if they meet the protocol specified definitions.
3. Elective/planned hospitalization(s) need not be reported as an SAE. However, complications or adverse events that occur during an elective/planned hospitalization, should be reported as (S)AEs if they meet the protocol specified definitions.
4. In the event of subject death during the conduct of the study, efforts should be made to perform an autopsy.
5. Sensations or side effects that occur during the programming session should not be reported as AEs. However, undesired sensations or side effects caused by the final programming parameters (including active contact, pulse width, frequency, and amplitude) that persist or occur after the completion of the programming should be reported as AEs.
6. Lack of efficacy/decreased therapeutic response should not be reported as AEs. Clinical sequelae, other than pain, that occur as a result of lack of efficacy/decreased therapeutic response should be reported as AEs
7. Clinically significant worsening of the pattern of intensity or distribution of Baseline pain symptoms should be reported as an AE.

8. Device deficiencies, including, but not limited to device/lead migrations, which are not associated with an adverse clinical outcome should only be reported as device deficiencies. However, if a device deficiency precipitates an AE, the AE should be reported in the Adverse Event eCRF and the device deficiency should be documented in the Device Deficiency eCRF.
9. If device implantation is unsuccessful, the subject will be followed for 2 weeks post implantation attempt to assess for procedure related adverse events. If the device is explanted, the subject will be followed for 30 days post explant to assess for related adverse events.

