**6.6. Safety Parameters**

[figure not shown]
Safety parameters include the rates of occurrence of all device hardware, device stimulation and procedure related non-serious adverse events, all serious adverse events, and unanticipated adverse events through the end of the study.

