### 7.2. Treatment Assignment

All enrolled subjects who pass eligibility criteria will receive a trial. Subjects with a positive trial will proceed to receive permanent implant. Following permanent implant, all subjects' device will be randomized in a 1:1 ratio to either receive:

- WaveWriter Settings – Perception and/or sub-perception programming with all available modalities
- Conventional Settings – Perception programming (up to 1.2 kHz)

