## **17. Safety Reporting**

### **17.1. Reportable Events by investigational site to Boston Scientific**

It is the responsibility of the investigator to assess and report to BSC any event which occurs in any of following categories:

- All Serious Adverse Events
- All Device Deficiencies
- Unanticipated Adverse Device Effects
- New findings/updates in relation to already reported events
- Device-hardware, device-stimulation, and procedure related non-serious adverse events

When possible, the medical diagnosis should be reported as the Event Term instead of individual symptoms.

If it is unclear whether or not an event fits one of the above categories, or if the event cannot be isolated from the device or procedure, it should be submitted as an adverse event and/or device deficiency.

Any AE event required by the protocol, experienced by the study subject after informed consent and once considered enrolled in the study (as defined in study subject classification section), whether during or subsequent to the procedure, must be recorded in the eCRF.

Underlying diseases are not reported as AEs unless there is an increase in severity or frequency during the course of the investigation. Death should not be recorded as an AE, but should only be reflected as an outcome of one (1) specific SAE (see Table 17.2-1 for AE definitions).

Refer to Directions for Use for the known risks associated with the commercial device(s).

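### Note 5 in Section 17.2 removes programming-session effects from AE reporting with no exception for serious events or for lasting effects of discarded settings, in conflict with Section 17.1

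*Combined protocol and SAP*

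**What the plan says.** Section 17.1 lists what sites must report. The list includes "All Serious Adverse Events" and "Device-hardware, device-stimulation, and procedure related non-serious adverse events", with no exception for programming sessions. It also sets a default: if it is unclear whether an event belongs to a listed category, "it should be submitted as an adverse event and/or device deficiency". Section 6.6 makes the rates of these events the safety parameters, including "all serious adverse events, and unanticipated adverse events through the end of the study".

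Note 5, below Table 17.2-1, has two sentences. The first is an exclusion: "Sensations or side effects that occur during the programming session should not be reported as AEs". The second restores part of what the first removes: "undesired sensations or side effects caused by the final programming parameters" are reportable if they are effects "that persist or occur after the completion of the programming should be reported as AEs".

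Notes 2 and 3 in the same list also contain exclusions, for planned procedures and elective admissions. Each adds that an event occurring in that setting is still reported if it meets the protocol's own definitions. Note 5 has no such clause.

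**The concern.** The exclusion in Note 5 depends on when an effect occurs, and the restoration depends on which setting caused it. Neither looks at seriousness. A programming session involves trying settings and rejecting some of them, so a rejected setting is by construction not among the final parameters. If it causes a serious effect, or one that continues after the session, a site following Note 5 to the letter records no AE, while Section 17.1 tells the same site to report it.

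What is at stake is the completeness of the SAE and stimulation-related AE listings. For serious events, so is the reporting clock in Section 17.4: 2 business days for a serious adverse device effect and 10 business days for an SAE.

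**Working it through.** No arithmetic applies. The documents give no rate of in-session events, no session count and no figure tied to this rule. The check is to set the passages side by side.

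**Inputs**
- Section 17.2, Note 5: exclusion and partial restoration, as above.
- Table 17.2-1: an AE is any untoward medical occurrence, with no session exception. An SAE is an adverse event that meets a seriousness criterion. An ADE is an adverse event related to device use. A SADE is an ADE with serious consequences. A UADE is defined directly as a serious effect or problem associated with the device and not previously identified; that definition does not use the AE term.
- Sections 17.1 and 6.6: the reportable categories and the safety parameters.

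**Chain of definitions.** If Note 5 removes AE status, the event cannot be an SAE or an ADE, and so cannot be a SADE. UADE status survives.

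**Cases under the literal text**
1. A transient effect that ends with the session is excluded. This is the evident purpose of the note and is reasonable.
2. An effect of the final settings that persists or begins after programming is reportable under the second sentence.
3. A non-serious effect of a tried-but-discarded setting that persists is excluded by the first sentence and not restored by the second. Section 17.1 requires it as a stimulation-related event. The two conflict.
4. An anticipated serious event from a discarded setting is excluded as an AE, and hence as an SAE and SADE. Section 17.1 requires all SAEs. The two conflict.
5. A serious unanticipated device effect in session is still reportable as a UADE, with its 1-business-day clock in Section 17.4 intact.

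**Do other routes catch cases 3 and 4?**
- UADE: only if the effect is unanticipated and serious. Neither case qualifies.
- Device deficiency: this needs an inadequacy of the device, which may include malfunction, use error or poor manufacturer information. A working device at a test setting may show none of these.
- Report-if-unclear default: this operates when the category is in doubt. A site that reads Note 5 as a specific instruction may see no doubt.

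**The case against.** The best case for leaving the text alone is that Note 5 speaks of sensations and side effects, not of injuries, admissions or SAEs. Its natural purpose is to keep the routine sensations of testing settings out of the database. An injury fits the AE definition directly, the ADE definition expressly covers operation of the device and use error, and Section 17.1 demands every SAE and leans toward reporting when in doubt. Many investigators would report a serious in-session event anyway. This shows that the gap may often be bridged in practice. It does not remove the contradiction: Notes 2 and 3 show that the authors wrote an explicit exception when they wanted one, and case 3 has no natural reading that rescues it.

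Three stronger readings are tempting, and the documents do not support them.
- A reader might infer that every in-session side effect is barred. The second sentence of Note 5 refutes that.
- A reader might infer that all fast reporting clocks are bypassed. The UADE clock is not.
- A reader might infer a safety comparison tilted toward the test arm, because Section 7.2 gives that arm "Perception and/or sub-perception programming with all available modalities" while the control arm has perception programming only. A wider choice of settings does not establish more serious in-session events. Both arms may use perception programming, no rates or session counts by arm are given, and from the 3-Month Visit (Section 10.11) all subjects may receive WaveWriter programming. Section 6.6 states safety as rates, and the unredacted text specifies no between-arm safety test. An uneven loss before 3 months is possible, but it is not shown.

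**Conclusion.** The point holds in a limited form. Note 5, followed literally, drops anticipated serious in-session events caused by settings not retained, and persisting effects of such settings. That contradicts Sections 17.1 and 6.6. It is a stated rule that gives the wrong result in identifiable cases, rather than a missing detail.

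The conclusion rests on the literal wording of Note 5 and on SAE, ADE and SADE being defined through the AE. How many events would be affected cannot be estimated from the documents, and no figure is offered. The matter concerns the completeness of safety reporting and is worth correcting because one missed serious event matters in an SAE listing. It has no bearing on the primary endpoint, alpha or power.

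**What to change.** Reconcile Note 5 with Section 17.1 in two steps.
1. Limit the exclusion to transient sensations or side effects that resolve when the setting is changed or the session ends.
2. Add the exception already used in Notes 2 and 3: an event during programming is reported as an AE or SAE if it meets the protocol's definitions, or if it persists after the session, whichever setting caused it.

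Serious in-session events then follow the Section 17.4 timelines without further change. Routine programming sensations stay out of AE reporting, so the purpose of the note is kept. The cost is one amended note, a notification to sites and probably a few additional reports.

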	Provide all relevant source documentation (de-identified/ pseudonymized) for reported event if requested by safety.	
 
• At request of sponsor
 

Adverse Device Effects	Complete AE eCRF page, which contains such information as date of AE, treatment of AE resolution, assessment of seriousness and relationship to the device.	
 
• In a timely manner (e.g. recommend within 30 business days) after becoming aware of the information
 
• Reporting of Adverse events which are device hardware, device stimulation and procedure related will be required through the end of the study.
 

	Provide all relevant source documentation (de-identified/ pseudonymized) for reported event if requested by safety.	

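### Note 7 in 17.2 requires worsening of Baseline pain to be reported whatever its cause, but a non-serious worsening judged unrelated falls outside 17.1, 17.4 and the visible 6.6 safety rates

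*Combined protocol and SAP*

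**What the plan says.** Section 17.2, Note 7, reads: "Clinically significant worsening of the pattern of intensity or distribution of Baseline pain symptoms should be reported as an AE". It does not ask whether the worsening is related to the device. Note 6, just before it, deals with failure or loss of benefit: "Lack of efficacy/decreased therapeutic response should not be reported as AEs". Its second sentence leaves pain out of the consequences to be reported: "Clinical sequelae, other than pain, that occur as a result of lack of efficacy/decreased therapeutic response should be reported as AEs".

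Section 17.1 lists what the investigator must report. All serious events are on the list. For non-serious adverse events the only entry is "Device-hardware, device-stimulation, and procedure related non-serious adverse events". The same section says of underlying disease: "Underlying diseases are not reported as AEs unless there is an increase in severity or frequency during the course of the investigation".

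The table in 17.4 applies the same limit: "Reporting of Adverse events which are device hardware, device stimulation and procedure related will be required through the end of the study". Section 6.6 defines the safety parameters as the "rates of occurrence of all device hardware, device stimulation and procedure related non-serious adverse events, all serious adverse events, and unanticipated adverse events".

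Two instructions favour capture. Section 17.1 tells sites to submit an event when its category is unclear or when it cannot be separated from device or procedure. Table 17.3-1 places an event in the possibly related class when its relationship cannot be assessed.

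**The concern.** Chronic pain is both the condition under treatment and the outcome of the trial, so pain that becomes worse than at Baseline is a direct harm. A site that follows Note 7 reports every clinically significant worsening. A site that follows the 17.1 list reports a non-serious worsening only if it judges it related. Even where the first site reports, 6.6 does not count the event unless it is related.

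The number of subjects shown as made worse then depends on which passage a site follows and on a causality judgement that is difficult for pain. The arms differ in whether stimulation is felt: 7.2 gives perception programming to the Conventional arm and perception and/or sub-perception programming to the WaveWriter arm. The judgement could therefore differ by arm. The primary claim does not fill the gap, because non-inferiority on the responder proportion with a margin of 0.20 says nothing about subjects whose pain rose above Baseline.

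**Working it through.** The plan gives no rate, threshold or safety sample size on this point, so there is no figure to reproduce. The check is to run the rules against the possible cases.

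| Case | Notes 6 and 7 (17.2) | 17.1 list and 17.4 | 6.6 rates |
|---|---|---|---|
| 1. Relief fades, pain not beyond Baseline | Note 6: not an event; Note 7 not triggered | Not required | Not counted |
| 2. Pain above Baseline, not clinically significant | Note 7 does not require it | Required only if related | Counted only if reported as related |
| 3. Clinically significant worsening beyond Baseline, put down to failed stimulation | Note 7: report; Note 6 can be read as excluding it | Depends on which note prevails | Depends on which note prevails |
| 4. Clinically significant, non-serious, relationship not assessable | Note 7: report | Submitted, classed as possibly related | Counted if that class is treated as related |
| 5. Clinically significant, non-serious, positively judged unrelated | Note 7: report | Not required | Not counted |
| 6. Worsening that meets the serious criteria | Report | Required | Counted |

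Case 1 is consistent. In case 2 the underlying-disease sentence in 17.1 sets a lower threshold than Note 7, but Note 7 can be read as the specific rule that refines it. Case 3 needs a statement of precedence between Notes 6 and 7. Case 6 has no gap.

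Case 5 is a real conflict, and nothing visible rescues it:

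- The instruction on unclear events and the possibly related default apply when the investigator cannot classify the event. They do not reach an event that has been classified. Table 17.3-1 allows the unlikely related class when another cause reasonably accounts for the event, and in this population the underlying condition is always a candidate.
- The same table allows an underlying illness as an alternative cause within the possibly related class, so one event can fall on either side. No visible text says which of the five classes count as related in 6.6.
- Section 6.6 also counts unanticipated events, but the unanticipated terms defined in Table 17.2-1 (UADE and USADE) both describe serious problems.
- Sections 10.10 and 10.11 collect the adverse events that the protocol requires, which leads back to the same list.

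The possible effect can be written down but not evaluated. Let W be the proportion of subjects with a non-serious Note 7 worsening and r the fraction of these judged related. Section 6.6 counts r × W and leaves out (1 − r) × W, which lies between 0 and W. If W is equal in both arms and r differs, the apparent difference between arms is (r in WaveWriter − r in Conventional) × W. The documents give neither W nor r.

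The underlying data exist. Table 10.1-1 schedules the pain NRS and VRS at Baseline, Programming Lock, 3 Months and later visits. The instrument named for the primary endpoint in 11.1.1, Percent Pain Relief on 0–100%, cannot as described record pain worse than Baseline.

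**The case against.** The strongest reply is that the passages do different jobs. Section 17.1 sets the reporting scope for all events, and Note 7 only clarifies that worsened pain can be an adverse event within that scope. Restricting non-serious events to related ones is applied in the same way in 6.6, 17.1 and 17.4, and it is a defensible choice for an approved device used under its Directions for Use. Leaving clinical significance to the investigator is also a legitimate choice; the lack of a threshold is missing detail and not an error in itself.

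Much of this stands. A reader might infer that Section 17 holds several irreconcilable rules for pain. The text does not support that: the underlying-disease sentence is an exclusion with an exception, which Note 7 can refine; Note 6 can be confined to loss of benefit down to Baseline; and the 17.1 list is not a rule about pain. What does not stand is that reading Note 7 within scope settles case 5. Note 7 says without condition that the worsening should be reported, no visible sentence subordinates it to the list, and 6.6 leaves the unrelated event out on either reading.

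It is also fair that the protocol has large redactions, including text between 6.3 and 6.6, within Section 11 and in 12.2, and that Appendix A, which governs new subjects, is not in the supplied text. A table of NRS change may exist there.

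**Conclusion.** The conflict holds for one defined group: non-serious, clinically significant worsening of pain beyond Baseline that is positively judged unrelated. Note 7 requires it to be reported, 17.1 and 17.4 do not, and the visible 6.6 rates do not count it.

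Three stronger conclusions are tempting and unsupported. A reader might put a multiple on the miscount; that would need a distribution of pain change, a threshold and an attribution fraction, none of which the documents give, and setting an unfiltered count against a related-only count would not compare like with like. A reader might infer that the arms are biased against each other; the difference in felt stimulation makes unequal attribution plausible, but nothing shows it. A reader might infer that worsening goes unrecorded; it is missing from the visible adverse event rates, while the NRS and VRS still record pain level at visits.

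The conclusion rests on the visible text for subjects enrolled under Versions A–C. The point does not affect the primary analysis. It is worth correcting because it changes which harms are counted.

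**What to change.** 1. Reconcile 17.1, 17.4 and Notes 6 and 7. State that Note 7 governs pain worse than Baseline and that Note 6 covers loss of benefit that does not go beyond Baseline. Add Note 7 worsening, whatever its relationship, to the 17.1 list, and match it in 17.4.
2. Add to 6.6 a descriptive by-arm table of randomized subjects whose NRS exceeds Baseline by an amount chosen by the sponsor, at the Programming Lock and 3-Month Visits, regardless of relatedness. Beside it, show the reported Note 7 events, which also cover change in distribution and worsening between visits, with the related subset beneath. State which classes of Table 17.3-1 make up that subset.

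The by-arm comparison should end with the 3-Month assessments, because 10.11 then allows all subjects WaveWriter programming. The same wording should be checked against Appendix A.

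The cost is wording in four places, a few more adverse event forms and one table from data already collected. The safety table may look slightly less favourable.

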**17.3. Relationship to Device(s)**

The Investigator must assess the relationship of the reportable AE to device-hardware, device-stimulation and/or procedure. See criteria in Table 17.3-1:

**Table 17.3-1: Criteria for Assessing Relationship of Study Device Hardware, Device Stimulation or Procedure to Adverse Event**

Classification	Description

Not Related Ref: MEDDEV 2.7/3
	
Relationship to the device or procedures can be excluded when:
 
 
- the event is not a known side effect of the product category the device belongs to or of similar devices and procedures;
 
- the event has no temporal relationship with the use of the study device or the procedures;
 
- the serious event does not follow a known response pattern to the medical device (if the response pattern is previously known) and is biologically implausible;
 
- the discontinuation of medical device application or the reduction of the level of activation/exposure - when clinically feasible – and reintroduction of its use (or increase of the level of activation/exposure), do not impact on the serious event;
 
- the event involves a body-site or an organ not expected to be affected by the device or procedure;
 
- the serious event can be attributed to another cause (e.g. an underlying or concurrent illness/ clinical condition, an effect of another device, drug, treatment or other risk factors);
 
- the event does not depend on a false result given by the study device used for diagnosis, when applicable; harms to the subject are not clearly due to use error;
 
- In order to establish the non-relatedness, not all the criteria listed above might be met at the same time, depending on the type of device/procedures and the serious event.
 

Unlikely Related Ref: MEDDEV 2.7/3
	
The relationship with the use of the device seems not relevant and/or the event can be reasonably explained by another cause, but additional information may be obtained.


Possibly Related Ref: MEDDEV 2.7/3
	
The relationship with the use of the study device is weak but cannot be ruled out completely. Alternative causes are also possible (e.g. an underlying or concurrent illness/ clinical condition or/and an effect of another device, drug or treatment). Cases where relatedness cannot be assessed or no information has been obtained should also be classified as possible.

Probably Related Ref: MEDDEV 2.7/3
	
The relationship with the use of the study device seems relevant and/or the event cannot be reasonably explained by another cause, but additional information may be obtained.

**Table 17.3-1: Criteria for Assessing Relationship of Study Device Hardware, Device Stimulation or Procedure to Adverse Event**

Classification	Description
Causal Relationship Ref: MEDDEV 2.7/3	
The serious event is associated with the study device or with procedures beyond reasonable doubt when:
 
 
- the event is a known side effect of the product category the device belongs to or of similar devices and procedures;
 
- the event has a temporal relationship with the study device use/application or procedures;
 
- the event involves a body-site or organ that 
 
-the study device or procedures are applied to;
 
-the study device or procedures have an effect on;
 
 
 
- the serious event follows a known response pattern to the medical device (if the response pattern is previously known);
 
- the discontinuation of medical device application (or reduction of the level of activation/exposure) and reintroduction of its use (or increase of the level of activation/exposure), impact on the serious event (when clinically feasible);
 
- other possible causes (e.g. an underlying or concurrent illness/ clinical condition or/and an effect of another device, drug or treatment) have been adequately ruled out;
 
- harm to the subject is due to error in use;
 
- the event depends on a false result given by the study device used for diagnosis, when applicable;
 
- In order to establish the relatedness, not all the criteria listed above might be met at the same time, depending on the type of device/procedures and the serious event.
 

